## Methodology

**Study Design:** This will be a randomized open label, delayed-start design trial conducted at Aga Khan University at Departments of: Biological & Biomedical Sciences, Pathology and Laboratory Medicine, Medicine (Endocrinology) and Family Medicine for a period of 2 years following approval from Clinical Trials Unit and Ethical Review Committee of Aga Khan University

**Sample Size calculation;** The sample size was calculated by PASS 11 software. In an equivalence test of means using two one-sided tests on data from two-periods, the minimum sample size that we will require is 142, 71 in each group with an inflation of 20% for loss to follow-up to achieve 80% power at a 5% significance level when the true difference between the means is 0.4, the standard deviation of the paired differences is 2.60.

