**Data Collection:** Randomization and drug dispensing will be followed by detailed history, physical examination, biophysical and biochemical parameters estimation by research team. The data will be collected on the following variables ; Body Mass index., Waist circumference (WC)Waist -Hip Ratio, Biochemical estimation ( results of following routine tests are available (Human Sex Hormone-Binding Globulin (SHBG), Total Testosterone (TT), Human Insulin and Glucose) to be included in the profile. For

[figure not shown]
estimation of Total Antioxidant Capacity (TAC), serum calcium and phosphorous levels, phlebotomist will collect blood samples (3 cc) by vein puncture).

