**Calculations;**

- i. HOMA-IR : HOMA- IR index, a commonly used marker of IR, will be calculated using the formula:  $\text{HOMA-IR} = \frac{\text{fasting glucose levels [mmol/L]} \times \text{fasting insulin levels } [\mu\text{U/mL}]}{22.5}$  (34).
- ii. Free Androgen Index will be derived from TT and SHBG, normally measured in nanomoles per liter.  $\text{FAI} = 100 (\text{TT} / \text{SHBG})$

**Outcome : Follow- up visits at 12 weeks (Study Mid Pont):** At 12 weeks follow up, compliance to supplementation and occurrence of any adverse effect will be assessed by research team allocated members in the respective clinics. Moreover, drug for 12 weeks (as per group allocation) will be dispensed and any other queries of participants will be responded. Fasting blood sample (10 ml) will be collected for estimation of SHBG, TT, Human Insulin, Glucose, serum calcium and phosphorous and TAC in both groups and VD and serum albumin estimation in Group A. At this point of time, **treatment protocol of both groups will be changed** (Table 2).

1. **Follow- up visits at 24 weeks (study End Point):** After completion of 24 weeks study exposure, subjects will be informed about completion of study. Blood samples in fasting state will be collected for repeat analysis in Multi Disciplinary Lab (MDL) for all the biochemical parameters (FAI, HOMA IR and TAC) and VD and serum albumin estimation in Group B. Figure 6: Complete cycle of each patient in control and intervention group for a period of 24 weeks

**Biohazardous Samples:** According to the WHO the serum samples have low viral concentration. However, the centrifugation is a risk for aerosol generation and COVID exposure. To minimize the risk, we will ; Train the research staff about the Basics of Biosafety, Biosecurity & Bio risk Management approach for collection & processing of samples. All samples will be treated as potentially infectious, use of proper PPE will be mandatory while handling samples. After centrifugation, staff will wait for 10 minutes before opening the centrifuge. In case of Breakage the already defined laboratory protocols (available in safety manual) will be followed. For liquid waste disposal, will use 5% Hypochlorite.

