Investigator and study coordinator will follow up any adverse events and serious adverse events.

**Plan of analysis:** Data will be analyzed using STATA version 15. The main analysis for each outcome will be performed at the subject level using the **intention-to-treat (ITT) principle**, meaning that all participants with a recorded outcome will be included in the analysis and will be analyzed according to the treatment group to which they were randomized. Results will be presented as mean and standard error/ median (IQR) for the outcomes. Pretreatment, 12 weeks and 24 weeks post treatment levels of the outcomes will be assessed by repeated measure ANOVA/ Friedman test as appropriate. Categorical variables will be reported as frequency and percentages and will be assessed by chi-square/ fisher exact test. Unadjusted and adjusted beta coefficient with 95% CI will be reported by using Generalized estimating equation (GEE) to determine the association of various independent factors with the outcomes. We will adjust for the independent variables and determine the association of factors causing a greater decline in outcomes by multivariable GEE. Plausible interactions and confounders will also be assessed. A p value of  $< 0.05$  will be considered as significant throughout the study

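### Each outcome gets its own main analysis at p<0.05 and no primary outcome or contrast is named, so the error rate of the efficacy conclusion exceeds the stated 5%

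*Protocol*

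**What the plan says.** In the Plan of analysis section, the protocol states: "The main analysis for each outcome will be performed at the subject level". It gives one test across visits per outcome: "Pretreatment, 12 weeks and 24 weeks post treatment levels of the outcomes will be assessed by repeated measure ANOVA/ Friedman test as appropriate". It then adds unadjusted and adjusted GEE coefficients for various independent factors, and says: "Plausible interactions and confounders will also be assessed". The section closes with one threshold, under which a p value below 0.05 "will be considered as significant throughout the study".

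The outcomes stand side by side. The 24-week visit repeats the blood analysis for "all the biochemical parameters (FAI, HOMA IR and TAC", and the 12-week sample supplies the same three quantities or their components. The Data Collection section also lists BMI, waist circumference and waist-hip ratio.

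The Sample Size calculation is framed as follows: "In an equivalence test of means using two one-sided tests on data from two-periods". Its inputs apply "when the true difference between the means is 0.4, the standard deviation of the paired differences is 2.60". It names no outcome and gives no equivalence margin.

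The Strength & Limitations section says that the trial will confirm the impact of vitamin D and predict when it should be given.

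**The concern.** A trial that intends to confirm an effect needs one stated test on which that conclusion rests, or a rule for combining several. The visible text has neither. Three biochemical outcomes from three domains (hyperandrogenism, insulin resistance, oxidative stress) have equal standing and the same threshold. The one place from which a primary outcome might be inferred, the sample-size paragraph, does not identify it.

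If the analysis follows the protocol as written, a significant result on any of the three can be reported as evidence of efficacy. The probability of such a report when vitamin D does nothing is then higher than 5%. The choice of which result to lead with could also be made after the data are seen.

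**Working it through.** **Inputs from the protocol**
- Threshold per test: 0.05 (Plan of analysis).
- Key outcomes: 3, namely FAI, HOMA-IR and TAC (24-week follow-up visit).
- Tests per outcome: 1, taking the repeated-measures ANOVA or Friedman test over baseline, 12 and 24 weeks as a single test.

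**Assumption.** The protocol gives no correlation between the test statistics, so a range from 0 to 0.9 is used.

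**Step 1. Does the sample size identify a primary outcome?** The figure of 142 cannot be reproduced from the stated inputs alone, because the equivalence margin is missing. For two one-sided tests on two-period data with SE = 2.60/√N, a true difference of 0.4 and an *assumed* margin of 1.0, N = 118 gives power 0.802. Then 118 × 1.2 = 141.6, or 142. That is a plausible route to the figure, but nothing in it points to a particular outcome.

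**Step 2. Three independent tests.** The chance of at least one p<0.05 under no effect is 1 − 0.95³ = 1 − 0.857 = 0.143.

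**Step 3. Three correlated tests.** For equally correlated normal statistics with correlation r and c = 1.96, the chance is 1 − ∫[Φ((c − √r·x)/√(1−r)) − Φ((−c − √r·x)/√(1−r))]³ φ(x) dx.

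| Assumed correlation | Chance of at least one false positive |
|---|---|
| 0 | 14.3% |
| 0.3 | 13.6% |
| 0.5 | 12.5% |
| 0.7 | 10.9% |
| 0.9 | 8.4% |

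Every row is above 5%.

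**Step 4. Further tests.** GEE factors and interactions are not limited in number. One additional independent test would raise 14.3% to 1 − 0.95⁴ = 18.5%.

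**Step 5. After correction.** With one primary outcome and one contrast at 0.05, the error rate of the efficacy claim is 5%. If the three outcomes stayed co-equal, Bonferroni at 0.05/3 = 0.0167 would give 1 − (1 − 0.0167)³ = 0.049 for independent tests.

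**Step 6. Can 0.4 and 2.60 be carried over to a two-sided between-arm test?** If 2.60 is read as a between-arm SD (an assumption; the protocol calls it the SD of paired differences), 80% power needs 2 × (1.96 + 0.842)² × 2.60² / 0.4² ≈ 664 per arm. Power is about 15% with 71 per arm, and about 13% with 59 per arm (71/1.2). The inputs cannot simply be transferred.

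**The case against.** The strongest reply is that the closing sentence is a conventional statement of the significance level. It does not say that p values will be unadjusted. A statistical analysis plan could apply Holm-adjusted p values or a fixed sequence at 0.05 without contradicting it, and multiplicity is often left to that document. This stands: the protocol does not rule out an adjustment. It does not answer the main point, because the choice of primary outcome and contrast belongs in the protocol, and the sample size depends on it.

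Three further points limit the finding.
- The protocol nowhere defines success as at least one significant outcome. A reader might infer such a rule, but it is not written. The calculation shows what the equal standing of the outcomes permits.
- The sentence about a main analysis for each outcome chiefly sets the analysis population. It is evidence of equal standing only because no other visible text ranks the outcomes.
- Part of the protocol between the cover letter and the Methodology was not available for this review. A primary objective stated there cannot be excluded.

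**Conclusion.** The point holds in a limited form. On the text at hand no outcome or contrast is primary, 0.05 applies to all, and the three key biochemical outcomes tested once each carry a false-positive chance of 8.4% to 14.3% over assumed correlations from 0.9 down to 0. The independent figure is the upper value. The result rests on all three being able to support an efficacy claim, and on no ranking in the unavailable part of the protocol.

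Larger figures are tempting but unsupported. A reader might infer that each outcome is tested separately at weeks 12 and 24, which would give 1 − 0.95⁶ = 26.5%. The protocol plans one test across all visits per outcome and states no separate test at each visit. A reader might also add BMI, waist circumference and waist-hip ratio at both visits, giving 1 − 0.95¹² = 46.0%. The follow-up visit descriptions mention blood tests, compliance and adverse effects, but no repeat body measurements.

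**What to change.** In the Plan of analysis section, replace the closing sentence on significance as follows.
1. Name one primary outcome and one primary between-arm contrast, tested at 0.05. Week 12 is preferable, because by week 24 both arms have received vitamin D.
2. Name the same outcome in the Sample Size calculation.
3. Test the other key biochemical outcomes as secondary by Holm's method. If their claims are to share the same 5%, test them only once the primary test has succeeded.
4. Report the remaining variables, GEE factors and interactions as estimates with 95% CIs and without significance claims.
5. Reconcile the sample-size hypothesis and inputs (equivalence, two-period data, SD of paired differences, no margin) with the chosen primary test, and restate the power.

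The first four changes are protocol wording. Their cost is a stricter threshold for the secondary outcomes: 0.05/2 = 0.025 at Holm's first step if two remain, or 0.05/3 = 0.0167 if three remain. The fifth may cost more. As step 6 of the working shows, the stated power could turn out much less favourable once the inputs match the primary test, and the sponsor should know this before fixing the choice.

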done using the permuted block randomization technique generating blocks with equal representation of all arms in a 1:1 ratio. The randomization list will be generated using the AKUH developed randomization software (<http://www.randomizer>). The randomization list is confidential and will be kept within the premises of CTU under restricted access. Subjects will be randomized into Group A (Intervention) and B (Control) and will receive the treatment protocol

**Intervention Group (Table 2) for the initial 12 weeks will receive:** VD supplementation (600,000 IU I/M) once during the study period and elemental calcium 1000 mg/day . However from 12-24 weeks they will receive standard PCOS treatment, lucophage XR 750 mg once at dinner for 15 days then twice daily, capsule Progeffik 100 mg once at night every 3 weeks, then 1 week off and calcium 1000 mg/day.

**Control Group for the initial-- 12 weeks** the control group will receive the standard treatment for PCOS , Glucophage XR 750 mg once at dinner for 15 days then twice daily and Capsule Progeffik 100 mg once at night every 3 weeks, then 1 week off

However, from 12- 24 weeks they will receive VD supplementation (600,000 IUI/M) once during the study period , calcium 1000 mg/day and standard PCOS treatment will be continued

	Group A (intervention)	Group B (Control)
Initial 12 weeks	Vitamin D: 1. VD supplementation (600,000 IU I/M once ) 2. Calcium 1000 mg/day	Standard PCOS; 1. Glucophage XR 750 mg once at dinner for 15 days then twice daily 2. Capsule Progeffik 100 mg once at night every 3 weeks, then 1 week off
At 12 weeks after consultation and biochemical tests treatment protocol will be changed as mentioned 
 
• Vitamin D & Calcium will be given to Group B with continuation of standard PCOS treatment (point of care)
 
• Standard PCOS care for Group A with continuation of calcium (point of care)
 
		
After 12 weeks	Standard PCOS; 1. Glucophage XR 750 mg once at dinner for 15 days then twice daily 2. Capsule Progeffik 100 mg once at night every 3 weeks, then 1 week off 3. Calcium 1000 mg/day (contd.)	Vitamin D: 1. VD supplementation (600,000 IU I/M) 2. Calcium 1000 mg/day 3. Standard PCOS Contd

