**Ethical Considerations:** In this research, we will adhere to ethical principles outlined in the Helsinki Declaration for medical research involving human subjects. We will seek approval from the Aga Khan Ethical Review Committee. The participants will be informed about the study's purpose and the possibility of being part of the intervention group based on computer randomization. We will obtain verbal and written consent from eligible participant. To ensure confidentiality, the entire process from participant enrollment to testing and outcome assessment will be handled discreetly. Consent forms and completed questionnaires will be assigned unique codes and securely stored in locked cabinets accessible only to the Principal Investigator. Participant identifiers will be removed, and only codes will be used in subsequent steps. Serum samples will be collected and coded without mentioning names. These samples will be processed at MDL-AKU and disposed of following AKU clinical lab's institutional policies for biological material disposal, which involves sealing them in red bags and incineration. Hard copies questionnaires will be stored and archived for a minimum of 7 years in line with AKU policy. Afterward, information will be deleted from computers, and the forms and questionnaires will be securely shredded. Results and data will be appropriately coded, decoded, and documented.

**Strength & Limitations:** The delayed-start design has **some methodological issues** in comparison with standard parallel-group study design of RCT. Nonetheless the effects of VD develop over time and we do not want to deprive VD deficient PCOS from VD supplementation in both groups, therefore we have selected this study design; **all subjects will be given same dose of VD either before or after standard PCOS care.** To the best of our knowledge this is the **first clinical trial** which will confirm not only the

impact of VD but also **predict the time of its administration**. Novelty of the study is that in addition to the routine parameters of IR and hyperandrogenism, this study will also estimate and document the **improvement in OS** as a result of the replacement therapy.

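### The regimens let the trial compare drug packages at week 12 and treatment sequences at week 24, so the claim to confirm the impact of vitamin D and predict its timing is not supported as written

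*Protocol*

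**What the plan says.** The Protocol's Intervention Group paragraph gives Group A "VD supplementation (600,000 IU I/M) once during the study period and elemental calcium 1000 mg/day" for the first 12 weeks, with no standard PCOS treatment. Over the same weeks Group B receives Glucophage XR and Progeffik, with neither VD nor calcium. At week 12 the "treatment protocol of both groups will be changed" (Outcome, follow-up visits at 12 weeks). Group A then starts the standard drugs and stays on calcium. Group B receives the VD injection, and for the rest the Control Group paragraph reads "calcium 1000 mg/day and standard PCOS treatment will be continued". The treatment table agrees with the text.

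Strength & Limitations presents the trial as the first that will confirm the impact of VD and also "predict the time of its administration". The cover letter puts the timing aim more softly, as a hoped-for insight. Strength & Limitations admits unspecified methodological issues with the delayed-start design and justifies the choice partly because "the effects of VD develop over time". It describes VD as given either before or after standard care.

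The Plan of analysis states: "Pretreatment, 12 weeks and 24 weeks post treatment levels of the outcomes will be assessed by repeated measure ANOVA/ Friedman test as appropriate". It adds GEE models with adjustment for independent factors, and says "Plausible interactions and confounders will also be assessed".

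**The concern.** Confirming the impact of VD requires a contrast in which VD differs and little else does. Predicting its timing requires a contrast in which only the time of giving it differs. The regimens appear to provide neither: calcium always travels with VD, and each randomised contrast also changes the amount of standard treatment. The same results could then be read as VD working or as VD doing nothing, depending on an assumption that is not written down. The conclusion at risk is the one the Protocol presents as the trial's distinctive contribution.

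**Working it through.** The plan gives no figure for this point, so there is none to reproduce. The check sets out what each arm has received by each visit and asks what the contrasts contain.

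**Exposure by visit** (from the Intervention Group and Control Group paragraphs and the treatment table, assuming each injection is given at the start of its 12-week period):

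| | Group A | Group B |
|---|---|---|
| Week 12: weeks since VD | 12 | not yet given |
| Week 12: weeks on calcium | 12 | 0 |
| Week 12: weeks on standard care | 0 | 12 |
| Week 24: weeks since VD | 24 | 12 |
| Week 24: weeks on calcium | 24 | 12 |
| Week 24: weeks on standard care | 12 | 24 |

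**Notation.** V(w), C(w) and S(w) are the effects w weeks after starting VD, calcium and standard care. T12 and T24 are changes over time common to both arms. Effects are taken as additive for illustration. Mean changes from baseline are then:

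- A, week 12: T12 + V(12) + C(12)
- B, week 12: T12 + S(12)
- A, week 24: T24 + V(24) + C(24) + S(12)
- B, week 24: T24 + V(12) + C(12) + S(24)

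**Randomised contrasts (A minus B).**

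- D12 = V(12) + C(12) - S(12)
- D24 = [V(24) - V(12)] + [C(24) - C(12)] - [S(24) - S(12)]

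V never appears without C. Four mean changes cannot determine eight unknowns (T12, T24 and six treatment effects). Counting the common baseline mean as well, the rank is 5 for 9 parameters.

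**Week 12 illustration.** The size 0.4 is borrowed from the Sample Size paragraph, which does not say which outcome it refers to, so it is only a convenient number.

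- Package V + C = 0, standard care S = 0.4: D12 = 0 - 0.4 = -0.4
- Package V + C = 0.4, standard care S = 0.8: D12 = 0.4 - 0.8 = -0.4

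A package with no effect and an effective one give the same contrast. Even if S were known, D12 would give only V + C: V = 0.4 with C = 0 and V = 0 with C = 0.4 look the same.

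**Week 24 illustration**, with calcium set to zero in favour of the claim, V(12) = 0.4 and S(12) = 0.4:

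- VD effect persists, standard care has levelled off: V(24) = 0.4, S(24) = 0.4, so D24 = 0 - 0 = 0
- VD effect lost, standard care has levelled off: V(24) = 0, S(24) = 0.4, so D24 = -0.4 - 0 = -0.4
- VD effect persists, standard care still growing: V(24) = 0.4, S(24) = 0.8, so D24 = 0 - 0.4 = -0.4

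The last two cases cannot be told apart. Serum VD would not settle it, because at week 24 the Protocol plans that measurement in Group B only.

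**Within-group changes.**

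- A, weeks 0 to 12: V(12) + C(12) + T12
- B, weeks 12 to 24: V(12) + C(12) + [S(24) - S(12)] + (T24 - T12)

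Both include calcium and a time trend with no concurrent control. B's also includes any further effect of continued standard care.

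**Adjustment.** Calcium and standard-care exposure are functions of arm and visit alone. A GEE covariate for either adds no information beyond arm and visit, so the fit cannot choose among these readings.

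**The case against.** The strongest reply is that Strength & Limitations itself frames timing as order, with VD given before or after standard care, and week 24 is a randomised comparison of two orders. Much of this stands. If VD acts differently before standard care than on top of it, that is arguably part of the question asked. A reader might infer that timing can be discussed only if VD and standard care do not interact, but the document's own framing does not support that condition. The unequal durations of calcium and standard care remain the difficulty.

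Other stronger readings also go too far:

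- **That the randomised comparisons are invalid.** They are not. Package against package and sequence against sequence are sound; only the attribution to VD or to its timing is unsupported.
- **That the analysis is built on before-after tests of Group A over weeks 0 to 12 and Group B over weeks 12 to 24.** The Plan of analysis names no such contrasts and no exposure coding. Its repeated-measures model could include group by time.
- **That subtracting the week-24 difference from the week-12 difference recovers a known share of the VD effect.** It does not without conditions on the other terms. With V(12) = V(24) = S(12) = S(24) = 0.4 and no calcium effect, D12 = 0 and D24 = 0, so the subtraction gives 0 although the VD effect is 0.4.

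It is also fair to say that the text at hand has no objectives section, that an unseen SAP might state assumptions, and that the target is one sentence in a paragraph that already concedes limitations. An SAP could state the assumptions, but it could not separate treatments that the regimens tie together. The concession names none of the issues set out here.

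**Conclusion.** The point holds as a mismatch between a stated conclusion and the regimens. Week 12 compares VD plus calcium with Glucophage XR plus Progeffik. Week 24 compares two sequences that differ in three durations at once. Neither isolates the effect of VD or of its timing, and no covariate adjustment changes that.

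The size is one of interpretation: in the illustration, a package effect of 0 and one of 0.4 both fit a week-12 difference of -0.4. The exposure table rests only on the regimens and on injection at the start of each period. The numbers rest on an additive model and a borrowed 0.4, and do not estimate any error in this trial. That the needed assumptions are unstated is established for the supplied Protocol text only.

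There is a related inconsistency. Strength & Limitations describes VD as before or after standard care, whereas the Control Group paragraph has Group B receiving it alongside continued standard care. These passages must be reconciled.

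**What to change.** In Strength & Limitations, and wherever conclusions are stated:

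1. Replace the claim about confirming impact and predicting timing with two comparisons: VD plus calcium against Glucophage XR plus Progeffik at week 12, and one treatment sequence against the other at week 24.
2. Label any within-group change that is reported (Group A weeks 0 to 12, Group B weeks 12 to 24) as an uncontrolled before-after estimate of VD plus calcium, and in Group B as added to continued standard care.
3. Attribute a difference to VD alone, or to its timing alone, only with the assumptions written out. For timing: the effects of unequal calcium and standard-care duration are nil or cancel. For before-after readings: no time trend and, in Group B, no further effect of continued standard care. These readings still cover VD and calcium together.
4. Reconcile the description of when VD is given relative to standard care with the Control Group paragraph and the treatment table.

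This is wording only. Treatments, visits, sample size and planned models are unchanged. The cost is a narrower headline claim.
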